#### 4.11 Standard of Truth (Cohort A only)

Histopathological diagnosis in patients undergoing radical prostatectomy. PSMA immunohistochemistry will be employed for exploratory analysis of Cohort A prostate specimens removed at surgery. Details of the planned histopathological analysis and the PSMA immunochemistry procedure are given in a separate Histopathology and Immunohistochemistry Manual prepared for this study.

### 5 TREATMENTS

#### 5.1 Investigational treatment

The test product in this trial is an F labelled PSMA ligand (F-rhPSMA-7.3) for i.v. administration, under development as a PET imaging tracer for the diagnosis and staging of PCa and possibly also other cancers manifesting increased expression of the target, PSMA, such as breast cancer. The IMP will be produced on-site at Turku PET Centre (TPC) according to the Scintomics platform F-rhPSMA-7.3 manual and TPC's SOPs.

Manufacturing, packaging and labelling of F-rhPSMA-7.3 will be performed in compliance with good manufacturing practice (GMP) regulations.

Each subject will receive a single F-rhPSMA-7.3 injection. For healthy volunteer subjects, the administered radioactivity will be approximately 225 MBq ( $\pm 10\%$ ). Their total radiation effective dose will not exceed 10 mSv. For subjects with PCa, the administered radioactive dose will be based on the results of the preliminary dosimetry analysis of the data obtained from the healthy volunteer subjects. Their total radiation effective dose will be 9.2 mSv; 300 MBq ( $\pm 10\%$ ) may be injected. The total maximum dose for both healthy volunteers and patients will be less than 100  $\mu$ g.

## 5.2 Reference treatment

Not applicable in this study.

## 5.3 Handling of the study product

Manufacturing, packaging and labelling of F-rhPSMA-7.3 will comply with GMP regulations and standard practices at and SOPs of TPC.

## 5.4 Prior and concomitant treatments

Prior medication refers to medication taken before the IMP administration. Medications used within 4 weeks prior to IMP administration should be recorded.

Concomitant medication is defined as any medication received by a subject after administration of the IMP until the end of the subject's participation in the study (30 days after IMP administration, end-of-study telephone contact).

## 5.5 Procedures for monitoring subject compliance

IMP administration will be performed by the study personnel. The study team member administering the IMP will ascertain and document that the IMP was administered according to the protocol. The compliance is assumed to be 100 %.

TPC will keep accurate written records of the production, quality control and administration of F-rhPSMA-7.3.

# 6 VISIT SCHEDULE

## 6.1 Screening

The screening period will begin up to 21 days before IMP administration. Each potential study subject will receive written and verbal information on the study and will have an opportunity to ask questions. If a subject decides to participate in the trial, written informed consent will be obtained before any study-related procedures are performed. A copy of the signed ICF will be provided to the subject.

At screening, a medical history interview will be conducted and a physical examination will be performed. Based on the subject's consent given in the ICF, any existing relevant medical records of the subject will be reviewed and copies thereof will be filed in the subject's source data file. Blood and urine samples will be collected for screening laboratory tests. Demographic data, body weight and height, 12-lead ECG and vital signs will also be recorded.

For a detailed description on the information to be collected during the screening period, please refer to Section 7.1.

[figure not shown]
A subject will be entered into the study only if all inclusion criteria and none of the exclusion criteria are met. All screening assessment results must be available before the decision to enrol a subject. Once the decision to enrol a subject has been made, a PET scan will be scheduled. Participation in the study should not delay the planned treatment of a subject with PCa.

## 6.2 Study periods

[figure not shown]
### Day 1

Before administration of the IMP administration/PET scan, a brief physical examination is performed, 12-lead ECG and vital signs (body temperature, respiration rate, supine systolic and diastolic BP and HR) and body weight are recorded, and blood and urine samples are collected for clinical laboratory tests. In addition, subjects will be asked about possible AEs which have occurred since consent was obtained and about new medications or changes to concomitant medications. AEs will also be monitored throughout the visit. The results of the physical examination, ECG, vital signs, AEs etc. must be reviewed for eligibility before the subject proceeds for the IMP administration and PET scanning. Healthy volunteers already suffering an AE on the day of the scan will be withdrawn or their IMP administration/PET scan visit will be postponed. Each subject will receive IMP as a single i.v. administration of F-rhPSMA-7.3.

After IMP administration, the healthy volunteer subjects will undergo a series of three CT attenuation-correction scans, each followed by multiple whole-body PET acquisitions. The minimum scanning data to be acquired for each healthy volunteer subject is the initial 1 to 90-min serial whole-body scan, 150 to 178-min mid-scan and the 220 to 248-min late scan, as illustrated in the figure below.

The subjects with PCa will undergo two CT attenuation-correction scans and dynamic PET imaging of the pelvic region (Cohort A; BCR patients in Cohort B; patients with biochemical progression in Cohort C) or the body region with one or more metastases defined as representative target lesions (metastatic patients in Cohort B and radiologically progressive patients in Cohort C) for 45 min, then 15 min break, and then multiple base of skull to mid-thigh PET acquisitions up to 118 min p.i. (see the figure below). The investigator will determine what the representative target lesions are in order to ensure that in the Cohort B and C patients all types of metastases, i.e. lymph node metastases, bone metastases, and soft tissue metastases, are represented on the dynamic images.

Once the scan acquisition is completed, the subject will be monitored for vital signs, ECG and AEs until at least 4 hr after IMP administration.

All procedures during the IMP administration day are presented in Table 2 (healthy volunteer subjects) and Table 3 (subjects with PCa).

**Table 2     Healthy Volunteer Schedule of Events: PET Imaging visit**

	Baseline (-120 to -5)	-5 min	IMP administration	+2 min	+5 min	+10 min	+15 min	+30 min	+60 min	+90 min	+180 min	+250 min
Physical examination	x											x
12 lead ECG	x	x								x	x	x
Continuous ECG monitoring (lead II)												
Body weight	x											
Vital signs (supine BP and HR, body temperature, respiration rate) a	x	x		x	x	x	x	x	x	x	x	x
Clinical laboratory tests	x b									x b	x b	x b
Urine analysis (stick test)	x											x
Pregnancy test for female subjects	x											
Drug abuse test	x											
Alcohol breath test	x											
IMP administration			x									
PET-CT imaging c												
Urine for  F radioactivity counting d												
Venous blood for  F radioactivity counting and % radioactive parent and metabolite analysis e												
Injection site monitoring												
AEs and SAEs	x											
Concomitant medications												

NOTE: Shaded areas depict continuous monitoring.

a Before vital signs are measured, the subject should be resting for at least 5 minutes.

b The safety laboratory parameter set. Please refer to Section 7.3.2.

c Total healthy volunteer PET acquisition time is 248 minutes (~4 hours). Please refer to Imaging Manual to see entire acquisition protocol with specific scanning time points.

d Urine will be collected in the following fractions as calculated from the time of F-rhPSMA-7.3 administration: until -5 min, -5 to 95 min, 95 to 185 min, and 185 to 255 min. The collection times are approximations and will depend on actual voiding times.e Blood samples will be taken at the following time-points as measured from the time of F-rhPSMA-7.3 administration: 30 sec, 60 sec, 90 sec, 4 min 30 sec, 5 min, 6 min, 7 min, 8 min, 15 min, 31 min, 47 min, 75 min, 120 min, 180 min, and 250 min after injection. Additional blood samples for radioactive metabolite analyses are taken at 5, 8, 15, 31 and 47 min after injection.

**Table 3      Prostate Cancer Patients Schedule of Events: PET Imaging visit**

	Baseline (-120 min to -5 min)	-5 min	IMP administration	+5 min	+10 min	+15 min	+30 min	+45 min	+120 min	+180 min	+240 min
Physical examination	x									x	
12 lead ECG	x	x						x	x	x	x
Continuous ECG monitoring (lead II)											
Body weight	x										
Vital signs (supine BP and HR, body temperature, respiration rate) a	x	x		x	x	x	x	x	x	x	x
Clinical laboratory tests	x b							x b		x b	x b
Urine analysis (stick test)	x										x
Drug abuse test	x										
Alcohol breath test	x										
IMP administration			x								
PET-CT imaging c											
Urine for  F radioactivity counting d											
Venous blood for  F radioactivity counting and % radioactive parent and metabolite analysis e											
Injection site monitoring											
AEs and SAEs											
Concomitant medications											

NOTE: Shaded areas depict continuous monitoring.

a Before vital signs are measured, the subject should be resting for at least 5 minutes.

b The safety laboratory parameter set. Please refer to Section 7.3.2.

c Total PCa patient PET acquisition time is 118 minutes (~2 hours). Please refer to Imaging Manual to see entire acquisition protocol with specific scanning time points.

d Urine will be collected in the following fractions as calculated from the time of F-rhPSMA-7.3 administration: until -5 min, -5 to 50 min, 50 to 125 min, and 125 to 240 min. The collection times are approximations and will depend on actual voiding times.e Blood samples will be taken at the following time-points as measured from the time of F-rhPSMA-7.3 administration: 20 sec, 40 sec, 60 sec, 80 sec, 100 sec, 120 sec, 140 sec, 160 sec, 180 sec, 4 min, 5 min, 7.5 min, 10 min, 15 min, 20 min, 30 min, 40 min, 50 min, 59 min and 120 min after the injection. Additional blood samples for radioactive metabolite analyses are taken at 5, 10, 20, 30, 40, and 50 min after injection.

### 6.3    Follow-up period

Day 2:

All subjects will visit the site 24 hours (+/- 6 hours) (Visit 2) after IMP administration for safety laboratory assessments, recording of 12-lead ECG and to collect information on concomitant medications and AEs.

### 30 Day Follow-up:

All subjects will be contacted by telephone at 30 days (+/- 2 days) after IMP administration to determine whether any AEs have occurred and to collect information on changes in concomitant medications. Additional study visits will be scheduled if needed for AE management. Any AEs will be followed up until resolution or stabilisation. In case of unanticipated delays in the planned surgical prostatectomy of the Cohort A PCa patients, the follow-up period of such subjects may be extended by up to 2 days to cover the surgery, and/or additional subjects may be enrolled into Cohort A in order to ensure that there are three evaluable subjects in Cohort A (see section 4.10 for criteria of evaluability).

## 7 ASSESSMENTS

### 7.1 Screening data

Information to be recorded during the screening period includes demographic and other baseline information and results of screening laboratory determinations.

#### 7.1.1 Demographic and other baseline information

Information to be recorded during the screening visit includes:

- subject's name, personal identity number, address; telephone number and e-mail address; none of this information is to be recorded on the CRF; personal identity number is collected due to laboratory logistics, on subject's permission given in the ICF;
- gender;
- race and ethnicity;
- height, weight, vital signs (supine BP and HR after 5 min rest, body temperature, respiration rate);
- 12-lead ECG;
- results of the physical examination (all main body systems according to site practice);
- habits (for the use of nicotine, alcohol, illicit drugs);
- information on previous diseases and current medical conditions;
- information on previous medications; all treatments used (including prescription medications, OTC medications, herbal remedies, trace elements and vitamins) within 4 weeks before the screening visit will be recorded;
- information on previous participation in clinical trials including PET trials or exposure to significant doses of ionizing radiation;
- blood and urine samples are collected for screening laboratory determinations;
- result of alcohol breath test and urine test for drugs of abuse;
- female reproductive status, information on menopause or surgical sterilisation and result of serum  $\beta$ -hCG pregnancy test;

- name and information of the subject's next-of-kin (not on CRF; this information will be removed from the subject's source data at end-of-study).

### 7.1.2 Screening laboratory determinations

All subjects will undergo blood and urine testing during the screening period. A study-specific Laboratory Manual will be available before study start. Screening laboratory tests include:

#### **Haematology:**

Haemoglobin  
Haematocrit  
Erythrocytes  
Leucocytes  
Mean corpuscular volume (MCV)  
Mean corpuscular haemoglobin (MCH)  
Platelets  
Neutrophils  
Eosinophils  
Basophils  
Lymphocytes  
Monocytes

#### **Chemistry:**

Alkaline phosphatase  
Alanine aminotransferase  
Aspartate aminotransferase  
Gamma-glutamyl transferase  
Albumin  
Total protein  
Total and conjugated bilirubin  
Creatinine  
Blood urea nitrogen (BUN)  
Chloride  
Potassium  
Sodium  
C-reactive protein  
Prostate specific antigen (PSA)  
Follicle Stimulating Hormone (FSH) and serum  $\beta$ -hCG pregnancy test (female volunteers only)

#### **Serology:**

HIVAgAb  
HBsAg  
HCVAg

**Clotting status:**

Partial Thromboplastin time (PTT)  
Activated partial thromboplastin time (aPTT)

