## 2.3 Primary endpoint

Safety is the primary endpoint of the study and it will be assessed from data on the occurrence of one or more treatment-emergent AEs from the time of i.v. administration of  $^{18}\text{F}$ -rhPSMA-7.3 throughout the study period, and changes in serum biochemistry, haematology, coagulation, urinalysis, vital signs, ECG, injection site status, and physical examination findings.

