### 7.3.2 Laboratory safety assessments

Please refer to Section 7.1.2 for laboratory safety assessments to be performed during the screening visit.

Day 1:

A urine pregnancy test (female subjects only), drug abuse test and breath alcohol test will be repeated before IMP administration.

During the IMP administration visit, sampling for the safety laboratory parameter set will be performed at baseline and at 90, 180 and 250 min post-injection (healthy volunteers) or at baseline, 45, 180 and 240 min post-injection (subjects with PCa). The safety laboratory parameter set will include all laboratory assessments described in Section 7.1.2, except for PSA, FSH, serum  $\beta$ hCG and the serology assessments.

Urine analysis will be performed at baseline and at 250 min post-injection (healthy volunteers) or at 240 min post-injection (subjects with PCa).

Day 2:

At the 24 hour follow-up visit, the safety laboratory parameter set will be repeated and will include all laboratory assessments described in Section 7.1.2, except for PSA, FSH, serum  $\beta$ hCG and the serology assessments.

The urine analysis will also be repeated.

Additional follow-up:

Additional laboratory safety assessments may be performed later as needed in the event of an AE or a safety variable being clinically significantly abnormal in the post-administration safety samples.

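### As written, the clotting panel lists PTT and aPTT and no prothrombin time, so the coagulation part of the primary safety endpoint would miss an isolated extrinsic-pathway change

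*Protocol*

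**What the plan says.** Protocol Section 7.1.2 introduces its test lists with "Screening laboratory tests include". The clotting status list has two entries: "Partial Thromboplastin time (PTT" and "Activated partial thromboplastin time (aPTT". Neither the other lists in that section, nor the rest of the protocol, nor its abbreviation list mentions prothrombin time, INR or any other extrinsic-pathway test.

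Section 7.3.2 builds the Day 1 panel by reference: "The safety laboratory parameter set will include all laboratory assessments described in Section 7.1.2". It removes PSA, FSH, serum β-hCG and serology, and adds nothing. Samples are taken "at baseline and at 90, 180 and 250 min post-injection (healthy volunteers) or at baseline, 45, 180 and 240 min post-injection (subjects with PCa". For Day 2 it says "At the 24 hour follow-up visit, the safety laboratory parameter set will be repeated".

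Section 2.3 defines the primary endpoint as treatment-emergent adverse events together with "changes in serum biochemistry, haematology, coagulation, urinalysis, vital signs, ECG, injection site status, and physical examination findings". Section 8.2.7 summarises each coagulation test descriptively, as actual values and change from baseline.

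**The concern.** A two-row coagulation panel would usually pair one test of the intrinsic pathway with one of the extrinsic pathway. Here both rows test the same side. The second row adds little, and the extrinsic pathway has no row at all. That suggests a wording slip, but the protocol does not settle it.

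The list matters beyond screening because Section 7.3.2 reuses it for all post-dose safety sampling. The report would tabulate two closely related variables under coagulation. It could then describe coagulation as unchanged when no test specific to the extrinsic pathway had been run. Safety is the primary objective, so what is measured limits what can be concluded.

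**Working it through.** The protocol states no figure to reproduce. The check is a trace through the text and a count of scheduled draws.

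**Trace**

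1. *What is listed.* Section 7.1.2, clotting status: PTT and aPTT.
2. *What is carried forward.* Section 7.3.2 takes the Section 7.1.2 list and drops four items, none of them a clotting test. The Day 1 and Day 2 coagulation panel is therefore the same two tests.
3. *What it feeds.* Coagulation is a named component of the primary endpoint (Section 2.3, and the same in the Synopsis). Section 8.2.7 analyses it as change from baseline.
4. *What the two tests read.* This step rests on general laboratory knowledge, not on the protocol. PTT and aPTT are the same assay without and with a contact activator. Both depend on the intrinsic and common pathways. A change confined to the extrinsic pathway (factor VII) alters neither; prothrombin time is the test that would show it.
5. *What else is in the panel.* Section 7.1.2 also lists ALT, AST, alkaline phosphatase, GGT, albumin, total protein, and total and conjugated bilirubin, taken at the same draws. aPTT itself depends on factors made in the liver. A marked fall in hepatic synthesis could therefore still show.

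**Count of draws that carry the clotting panel**

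| Occasion | Draws per subject |
|---|---|
| Screening | 1 |
| Day 1 baseline | 1 |
| Day 1 post-dose (90, 180, 250 min in healthy volunteers; 45, 180, 240 min in patients) | 3 |
| 24-hour visit | 1 |
| **Total** | **6** |
| **Post-dose only** | **3 + 1 = 4** |

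Sections 4.2 and 8.1 plan 15 evaluable subjects:

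- all draws: 6 × 15 = 90
- post-dose draws: 4 × 15 = 60

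These are planned minimums. Section 8.2.3 analyses safety in everyone who receives the product, and Section 4.10 allows additional subjects to substitute for non-evaluable ones. Each additional dosed subject who completes the schedule adds 6 draws, 4 of them post-dose. The counts show how many scheduled draws the gap reaches; they do not measure information lost.

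**The case against.** The strongest reply is that this is a slip and not a design decision. Section 7.1.2 announces a study-specific Laboratory Manual, which is not at hand, and the laboratory may run a prothrombin time under it. The word introducing the lists could also be read as non-exhaustive. This stands in part. A reader might infer that no prothrombin time will be obtained in the trial; the protocol supports only that none is listed. It does not remove the point. If the manual specifies prothrombin time, the two documents disagree and Section 7.1.2 needs correcting. If the manual follows Section 7.1.2, the test is not run. Since Section 7.3.2 defines the post-dose set by what Section 7.1.2 describes, a test not described there is not in the set. An analysis plan cannot recover an assay that was not done.

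A second reply is that impaired hepatic synthesis would not go unnoticed. This stands. A reader might infer that the panel is blind to it, but aPTT depends partly on liver-made factors, and albumin, bilirubin and liver enzymes are measured at the same draws. Sensitivity is reduced, not lost.

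A third reply is that the stakes are small. This also stands. Section 5.1 specifies a single administration of less than 100 µg, Section 8.2.2 states no formal hypotheses, and coagulation is one item in a broad safety description.

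Two further inferences should be resisted. One is that half of the coagulation endpoint goes unmeasured: Section 2.3 prescribes no panel, and the common pathway is covered. The other is that Cohort A patients are exposed at prostatectomy: that surgery is scheduled care, and nothing in the protocol makes this panel the pre-operative work-up.

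**Conclusion.** The point holds in a limited form. As written, the coagulation component of the primary safety endpoint rests on two versions of one assay at all 6 scheduled draws per subject, 4 of them post-dose (at least 90 and 60 over 15 evaluable subjects). It would miss an isolated extrinsic-pathway change and is less sensitive than it could be to impaired hepatic factor synthesis. The most likely explanation is that the first entry was meant to be prothrombin time.

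The impact is modest: the analysis is descriptive, and no hypothesis, sample size or decision rule depends on this component. The conclusion assumes that the usual understanding of the two assays applies at the study laboratory and that the Laboratory Manual does not add a prothrombin time. If the manual does add one, what remains is a discrepancy between documents rather than a gap in measurement.

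**What to change.** Check the clotting list in Section 7.1.2 against the Laboratory Manual. Replace the PTT entry with prothrombin time (PT/INR), keep aPTT, and make the manual agree. Sections 7.3.2 and 8.2.7 refer to the list and need no further edit.

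If the panel is kept as it stands, state why and limit any conclusion on coagulation to the intrinsic and common pathways. The same limit applies to any subjects already sampled without a prothrombin time.

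The cost is one protocol line, a matching check of the manual, and a one-for-one swap of a routine assay on the coagulation sample already drawn. No extra draw or visit is needed.

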**Urine analysis:**

- Stick test: pH, erythrocytes, leukocytes, nitrite, protein, glucose, ketones; microscopy and bacterial culture will be performed if indicated by the stick test results;
- Urine test for drugs of abuse: tetrahydrocannabinol, amphetamine, morphine and related opioids, benzodiazepines, methamphetamine, ecstasy, buprenorphine, tramadol, methadone, fentanyl, oxycodone.

**Alcohol breath test:** Alcotest 6510 test system

## 7.2 Assessment of efficacy

### 7.2.1 Standardised Uptake Values (SUVmax, SUVmean, SUVR)

- SUV (standardised uptake value) is a ratio of tissue radioactivity concentration and administered dose of radioactivity divided by body weight:
- SUV = activity (Bq/g)/[injected activity (Bq)/body weight (g)]
- SUVmax is the maximum standardized uptake value.
- SUVmean is the mean standardized uptake value.
- SUVR is a ratio of SUV in a detected lesion and SUV of a reference tissue, such as blood.

Data will be presented graphically to evaluate the optimal imaging time post-injection.

